## PROTOCOL SYNOPSIS

**Gilead Sciences, Inc.**  
**[name]**  
**[name]**

---

**Study Title:** A Phase 2, Open-Label Study to Investigate the Safety and Efficacy of Sofosbuvir/Velpatasvir Fixed Dose Combination Administered for Four Weeks in Patients Infected with Chronic HCV in the Peri-Operative Liver Transplantation Setting

---

**IND Number:** This is a non-IND study

**EudraCT Number:** Not Applicable

**Clinical Trials.gov Identifier:** Not Available

---

**Study Centers Planned:** Approximately one center in New Zealand

---

**Objectives:** The primary objectives of this study are as follows:

- To explore the antiviral efficacy of treatment with sofosbuvir/velpatasvir (SOF/VEL) fixed-dose combination (FDC) therapy administered for four weeks following liver transplantation as measured by sustained virologic response (SVR) 12 weeks after cessation of treatment (SVR12)
- To evaluate the safety and tolerability of SOF/VEL in HCV-infected subjects in the peri-operative and post-transplant period

The secondary objectives of this study are as follows:

- To determine the percentage of subjects who attain SVR at 4 weeks after cessation of treatment (SVR4)
- To evaluate the proportion of subjects with virologic failure
- To assess rates of graft survival, graft function, acute rejection and immunosuppressive therapy during treatment with SOF/VEL
- To evaluate the emergence of viral resistance to SOF and VEL during treatment and after cessation of treatment
- To evaluate the kinetics of circulating HCV RNA during treatment and after cessation of treatment
- To characterize pharmacokinetics of SOF/VEL

The exploratory objectives of this study are as follows:

**PPD**

**Study Design:**

This is an open-label study that will evaluate the safety, tolerability and antiviral efficacy of SOF/VEL administered for 4 weeks in HCV-infected adult male and female subjects who are undergoing liver transplantation.

For all subjects SOF/VEL tablet (400/100 mg) once daily will be started the day of the subject's liver transplant if the transplant is completed before noon and the following day if it is completed after noon and will continue for 4 weeks. Treatment initiation may be delayed for up to 1 day if warranted by the subject's medical condition post-surgery.

HCV RNA will be assessed at each visit.

**Sub-Study:**

**Pharmacogenomics (PG) Sub-study**

**PPD**

**Pharmacokinetic (PK) Sub-study (Required)**

All subjects will participate in a PK sub-study in which intensive serial PK sample collection (samples obtained over 24 hours) will be performed on Day 1 to determine pharmacokinetics of SOF, its metabolites GS-566500 and GS-331007, and VEL.

**Number of Subjects Planned:**

Approximately 10

**Target Population:**

HCV infected adults who are undergoing primary liver transplantation

**Duration of Treatment:**

Subjects will be treated for 4 Weeks

**Diagnosis and Main Eligibility Criteria:**

HCV infected, male and non-pregnant/non-lactating female subjects, ages 18 years or older, who are undergoing liver transplantation, may be eligible for the study.

Reference Section 4.2 and 4.3 of the protocol for detailed Inclusion and Exclusion criteria.

Study Procedures/  
Frequency:

Screening assessments will be completed at the time a subject is identified as a potential study participant to give sufficient time for the subject to provide informed consent and perform screening assessments. Subject's screening data will be confirmed in the pre-operative period (within 48 hours of the planned transplant) at the Pre-surgery visit if the screening visit occurs more than 48 hours before the liver transplant surgery is started.

All subjects will complete the following study visits: Screening; Pre-surgery (if needed); On-Treatment visits Days 1, 3, 5, 7, 14, 21, and 28; and Post-treatment Visits at Weeks 1, 2, 4, and 12 following the last dose of study drug.

After consent is obtained, initial screening assessments will include physical examination, medical history, height (initial screening only), weight, vital signs, resting 12-lead electrocardiogram (ECG), screening procedure-related adverse events (AEs), concomitant medications (CMs), CPT and MELD score, safety laboratory tests (including hematology, chemistry, and coagulation), estimated creatinine clearance ( $Cl_{cr}$ ), HCV RNA, HCV genotype, serology (HIV, HCV, HBV), serum  $\beta$ -hCG (females of child bearing potential only), and urinalysis.

If the screening visit occurs more than 48 hours before the liver transplant surgery is started, the subject will also be reassessed within 48 hours of transplantation to determine their continued eligibility at the pre-surgery visit. The assessments will include physical examination, re-review of the medical history, weight, vital signs, resting ECG, AEs, CMs, CPT and MELD score, safety laboratory tests, estimated  $Cl_{cr}$ , HCV RNA, urine pregnancy tests (females of childbearing potential only) and pregnancy prevention counseling.

If a separate informed consent is signed, samples of the explanted liver will be taken during surgery.

If the transplant is completed before noon, the subject will take their first dose that day after the transplant which will be considered Day 1. If the transplant is completed after noon, the subject will take their first dose the following morning which will be considered Day 1. The planned first dose may be delayed for up to 1 day if, in the investigators opinion, delay is in the subject's medical interest. The subject will receive 4 weeks of study drug.

On-treatment assessments starting at Day 1 will include vital signs, ECG (only at Day 28), AEs, CMs (including immunosuppressive therapy), safety laboratory tests, estimated  $Cl_{cr}$ , HCV RNA, study drug dosing adherence and urine pregnancy tests (females of childbearing potential only).

Post-treatment assessments through Post-treatment week 4 only include AEs and CMs. Weight, vital signs, and urine pregnancy tests (females of child bearing potential only) will only be done at Post-treatment week 4. Pregnancy prevention counseling will be done at Post-treatment week 1 only. Safety laboratory tests, HCV RNA and viral sequencing samples will be collected through all Post-treatment visits.

Samples for viral RNA sequencing/phenotyping will be collected starting at Day 1 and every visit thereafter.

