## 1.8. Rationale for This Study

This is a Phase 2 study designed to evaluate the efficacy and safety of the SOF/VEL tablet administered for 4 weeks to subjects starting in the perioperative period of liver transplantation.

After transplantation, recurrence of HCV infection occurs in almost all patients {Feray et al 1992}, {Wright et al 1992} who have HCV RNA detectable prior to transplantation. HCV recurrence is associated with cirrhosis, fibrosing cholestatic hepatitis, graft loss, liver re-transplantation, and death {Prieto et al 1999}, {Wiesner et al 2003}, {Berenguer et al 2002}, {Gane et al 2008}, {Crespo et al 2012}, {Charlton et al 2014}, {Berenguer et al 2000}, {Forman et al 2002}, {Firpi et al 2009}. HCV RNA levels fall significantly in the anhepatic phase of liver transplantation and continue to fall during the first 12-24 hours post transplantation. Serum HCV RNA then begin to rise rapidly from the second post-operative week and peak by the fourth month {Charlton 2003}.

Deposition of fibrotic tissue in most HCV transplanted livers is highly accelerated with the development of bridging fibrosis and cirrhosis in 20-54% at 5 years and 32-51% at 7 years {Berenguer et al 2013}. Once cirrhosis is established, the probability of liver graft failure is 42% within 12 months {Berenguer et al 2002}.

There is great advantage to administering a well-tolerated direct acting antiviral without the use of PEG-IFN or RBV in the immediate postoperative period while the HCV RNA virus is at its lowest level. We hypothesize that the time period prior to re-infection is unique and mimics that of acute infection, as the nidus of HCV chronic infection (pretransplant liver) has been removed. For this reason, we believe that a short course of therapy (eg, 4 weeks), is likely to be successful. If the progression of the HCV virus can be halted before the progressive liver fibrosis activity is initiated both the new graft and the patient stand a greater chance of survival.

Additionally, patients who start HCV treatment pre-transplant may not have time to complete the full duration of treatment when a liver becomes available. The results of this study can inform on the safety and efficacy of continuing SOF/VEL treatment through transplantation.

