## 2. OBJECTIVES

The primary objectives of this study are:

- To explore the antiviral efficacy of treatment with SOF/VEL FDC therapy administered for four weeks following liver transplantation as measured by sustained virologic response 12 weeks after cessation of treatment (SVR12)
- To evaluate the safety and tolerability of SOF/VEL in HCV-infected subjects in the peri-operative and post-transplant period

The secondary objectives of this study are:

- To determine the percentage of subjects who attain SVR at 4 weeks after cessation of treatment (SVR4)
- To evaluate the proportion of subjects with virologic failure
- To assess rates of graft survival, graft function, acute rejection and immunosuppressive therapy during treatment with SOF/VEL
- To evaluate the emergence of viral resistance to SOF and VEL during treatment and after cessation of treatment
- To evaluate the kinetics of circulating HCV RNA during treatment and after cessation of treatment
- To characterize pharmacokinetics of SOF/VEL

The exploratory objectives of this study are:

PPD

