### **6.9.11. Viral RNA Sequencing / Phenotyping Sample**

Plasma samples will be collected at Day 1 and at each visit for viral sequence analysis. At any unscheduled visit initiated for the purpose of confirming virologic breakthrough or relapse, a plasma sample for viral sequence analysis must be collected. Untested samples may be archived.

Details regarding the collection, processing, and shipping of samples will be included in the lab manual.

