**Appendix 2. Study Procedures Table**

**Appendix Table 1. Screening, On-Treatment Visits**

Clinical Assessments	Screening	Pre-Surgery (if more than 48 hours from screening to transplant)	Day 1 a	Days on Treatment (±2 days)						ET/ Unscheduled e
				3	5	7	14	21	28	
Informed Consent	X									
Determine Eligibility	X	X								
Medical History	X	X								
Physical Examination	X	X								X
Height and Weight b	X	X	X							X
Vital Signs c	X	X	X	X	X	X	X	X	X	X
12-lead ECG d	X	X								
CPT and MELD Scores	X	X								
Adverse Events and Concomitant Medications	X	X	X	X	X	X	X	X	X	X
Pregnancy Prevention Counseling	X	X	X							X
Hematology & Chemistry	X	X	X	X	X	X	X	X	X	X
Coagulation (PT, PTT and INR)	X	X	X	X	X	X	X	X	X	X
CrCL calculation	X	X	X	X	X	X	X	X	X	X
HCV RNA (Plasma) e	X	X	X	X	X	X	X	X	X	X
Viral RNA Sequencing /Phenotyping Sample (Plasma)			X	X	X	X	X	X	X	X
Single Pharmacokinetic Sample						X	X	X	X	X
Pregnancy Testing f	X	X	X						X	X
Urinalysis	X	X								

Clinical Assessments	Screening	Pre-Surgery (if more than 48 hours from screening to transplant)	Day 1 a	Days on Treatment (±2 days)						ET/ Unscheduled c
				3	5	7	14	21	28	
IL28B Genotype			X							
HCV Genotype	X									
HCV, HIV, HBV Serology	X	X								
Archive Sample g			X						X	X
PPD										
PK Sub-study Collection i			X							
Study Drug Dosing			X	X	X	X	X	X	X	
Review of Study Drug Adherence and Drug Accountability j				X	X	X	X	X	X	X

- a If the transplant is completed before noon, the subject will take their first dose that day after the transplant which will be considered Day 1. If the transplant is completed after noon, the subject will take their first dose the following morning which will be considered Day 1. The planned first dose may be delayed for up to 1 day if, in the investigators opinion, delay is in the subject's medical interest. ET = Early Termination; at all unscheduled visits initiated for the purpose of confirmatory testing, a viral sequence analysis plasma sample must be obtained.
- b Weight should be done with inner clothing and without shoes and Height should be done at screening only. Height will be performed only at initial screening visit. Weight will be assessed at screening and Day 1 for CrCL calculations. CrCL calculation for all post-transplant visits will use the Day 1 weight.

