- c Vital signs include resting blood pressure, pulse, respiratory rate and temperature.
- d Subjects will be required to rest in a supine position for ≥ 5 minutes prior to making a recording. The investigator (or qualified designee) should review the ECG traces recorded in real time for gross abnormalities.
- e HCV RNA samples will be collected at all visits. An additional HCV RNA sample will be collected just before but as close to the transplant as possible.
- f For females of childbearing potential only: serum β-hCG at Screening, urine test thereafter. If urine is positive, confirm immediately with serum β-hCG. .

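### The only scheduled pretreatment viral-sequencing sample is on Day 1, after the infected liver is removed, so a failure whose Day 1 sample cannot be sequenced could not be assessed for emergent resistance

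*Protocol*

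**What the plan says.** Protocol Section 2 lists as a secondary objective: "To evaluate the emergence of viral resistance to SOF and VEL during treatment and after cessation of treatment".

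Three places set the sequencing schedule:
- The Synopsis (study procedures): "Samples for viral RNA sequencing/phenotyping will be collected starting at Day 1 and every visit thereafter".
- Section 6.9.11: "Plasma samples will be collected at Day 1 and at each visit for viral sequence analysis".
- Appendix Table 1: the sequencing row is marked at Days 1, 3, 5, 7, 14, 21, 28 and the early-termination/unscheduled column. Screening and Pre-Surgery are blank.

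Day 1 always comes after the transplant. The Synopsis says: "If the transplant is completed before noon, the subject will take their first dose that day after the transplant which will be considered Day 1". For surgery ending after noon, Day 1 is the next morning, and the first dose may be put back by up to one further day.

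On viral load at that time, Section 1.8 says: "HCV RNA levels fall significantly in the anhepatic phase of liver transplantation and continue to fall during the first 12-24 hours post transplantation". It argues for starting treatment "in the immediate postoperative period while the HCV RNA virus is at its lowest level".

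Blood for HCV RNA is drawn before transplant, at Screening and at Pre-Surgery where that visit occurs. Footnote e of Appendix Table 1 adds: "An additional HCV RNA sample will be collected just before but as close to the transplant as possible". None of these draws is assigned to sequencing.

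On analysis, SAP Section 6.2.2 says only that resistance substitutions will be discussed in the study report.

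**The concern.** A variant seen at failure can be called emergent only by comparison with a sequence from before treatment. The plan provides one scheduled sample for that purpose. It is taken when, by the protocol's own rationale, there is little circulating virus to sequence. The feature that supports starting treatment then also puts the reference sample at risk.

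Nothing else in the documents guarantees a substitute. The archive sample is optional and also begins on Day 1. Explant tissue needs a separate consent. The genotype assay at Screening (Section 6.9.1) gives genotype and subtype and is not assigned to resistance. Samples after Day 1 are on or after treatment. Section 6.9.11 does not say that the Day 1 sequencing sample is drawn before the first dose.

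At stake is the reading of individual failures after a 4-week course: whether a resistance variant was selected by treatment or was already there.

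**Working it through.** **The plan's own figure.** The only design figure is the 63% maximum length of the exact 95% interval with 10 subjects (Protocol 8.8, SAP 1.3). The Clopper-Pearson interval is widest at 5 of 10: 18.7% to 81.3%, length 62.6%, which rounds to 63%. It reproduces, and this point does not depend on it.

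**Step 1: is any pre-transplant sequencing sample scheduled?** Taken alone, the each-visit wording in Section 6.9.11 could include pretreatment visits. The Synopsis starts the series at Day 1, and the Appendix Table 1 cells before Day 1 are blank. Read together, the first assigned sample is Day 1.

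**Step 2: does a pretreatment sequence matter?** The Phase 3 summaries in the protocol rely on one.
- Baseline NS5A variants: 16% (Section 1.6), 26-29% (1.7), about 42% (1.4) and about 60% (1.5, genotype 2 only).
- Baseline NS5B variants: 4% (1.6), about 9% (1.4) and about 10% (1.5).
- In the decompensated-cirrhosis study (1.7), 6 genotype 1 failures had NS5A variants at failure, of which 5 were emergent and 1 was maintained from pretreatment. All 13 genotype 3 failures had Y93H, of which 10 were emergent. Not emergent: (1 + 3)/(6 + 13) = 4/19 = 21%. That the 3 genotype 3 cases were pre-existing is inferred; the text does not say so directly.

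**Step 3: how many subjects could be affected?** Let f be the virologic failure rate and q the probability that a Day 1 sample cannot be sequenced. The documents give neither, so both are assumptions, and f and q are treated as independent.

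Expected failures without a baseline sequence = 10 × f × q. Chance of at least one = 1 − (1 − f × q)^10.

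| f | q | Expected number of 10 | Chance of at least one |
|---|---|---|---|
| 10% | 20% | 0.2 | 1 − 0.98^10 = 18% |
| 10% | 60% | 0.6 | 1 − 0.94^10 = 46% |
| 30% | 20% | 0.6 | 1 − 0.94^10 = 46% |
| 30% | 60% | 1.8 | 1 − 0.82^10 = 86% |

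**Step 4: why q cannot be fixed from the documents.** Suppose sequencing needed 1,000 IU/mL (assumption). A subject at 800,000 IU/mL before transplant would drop below that only after a fall of log10(800,000/1,000) = 2.9 log10. A subject at 10,000 IU/mL would do so after a fall of 1.0 log10. The size of the fall by Day 1 is not stated.

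**The case against.** The strongest reply is that the documents show a low point but not a sample too weak to sequence. Lowest is relative, and a fall from a high level may leave enough template. This stands, and it is why no frequency can be claimed.

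Other points also stand in part:
- HCV RNA keeps falling for 12-24 hours, so a Day 1 sample on the day of surgery may precede the nadir. A reader might infer that Day 1 is the worst possible time; the text supports only at or near the lowest level.
- Day 1 virus is the closest to what the drug actually meets, and the wait for an organ is variable (SAP 1.2), so a Screening sample may be old. This is a reason to keep Day 1, not to rely on it alone.
- A missing baseline matters only for virologic failures, and chiefly those with variants. In the decompensated-cirrhosis study, 3 of 9 genotype 1 failures had no NS5A variant at failure. A failure with no variant in either target needs no baseline to show that none emerged.
- Protocol 8.1.5 places resistance among other endpoints of interest, with no planned test. It is nevertheless a stated secondary objective.
- The archive and explant substudy text is redacted, the laboratory manual is not available, and leftover pre-transplant plasma may be kept. A fallback may therefore exist; the documents do not assign one.

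A reader might take the 20-60% loss to mean that 2 to 6 of 10 subjects are lost to the resistance analysis. That counts subjects who respond and need no comparison at failure, and it rests on a rate that no document figure supports.

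**Conclusion.** The point holds as a gap in the sampling schedule. The only sample assigned as a pretreatment sequence is taken after hepatectomy, at or near the HCV RNA low point described in the protocol's own rationale, and neither document names a fallback.

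The consequence is subject by subject. For a virologic failure without a usable Day 1 sequence, NS5A or NS5B variants found at failure could not be classed as emergent or pre-existing. Under the assumed 20-60% loss and 10-30% failure rate, that is about 0.2 to 1.8 of 10 subjects. The true frequency is unknown.

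A reader might go further and conclude that the resistance objective would be left unanswered. The documents do not support that: it would fail entirely only if every failure that needed a baseline lacked one. This is a cheap improvement, not a flaw that threatens the trial. SVR12, its interval and the sample size are unaffected.

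**What to change.** - In Appendix Table 1, Section 6.9.11 and the Synopsis, assign a sequencing/phenotyping plasma aliquot to the existing pre-transplant HCV RNA draws: Screening, and either Pre-Surgery or the draw just before transplant. The last of these is the most useful, because it is closest to transplant and does not depend on whether a Pre-Surgery visit occurs.
- Keep the Day 1 sequencing sample and state that it is drawn before the first dose.
- In the SAP, define the pretreatment reference as the last sequenceable sample before the first dose, falling back to the latest pre-transplant sample if Day 1 cannot be sequenced. Report which sample was used for each failure.

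The cost is one extra aliquot per draw, storage, a laboratory-manual change and a minor amendment. No visit is added and clinical management does not change.

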**PPD**

---

**Test Product, Dose, and Mode of Administration:**

SOF/VEL is manufactured as a FDC tablet, consisting of 400 mg SOF and 100 mg of VEL, for oral administration. Subjects will take 1 tablet daily with or without food.

---

**Reference Therapy, Dose, and Mode of Administration:**

None

---

**Criteria for Evaluation:**

**Safety:** AEs and safety laboratory tests will be collected throughout the study (through the Post-treatment week 4 visit).

**Efficacy:** Efficacy will be evaluated using scheduled assessments of HCV RNA performed using Roche COBAS® AmpliPrep/COBAS® TaqMan® HCV Test, v. 2.0.

**Pharmacokinetics:** A single PK blood sample will be collected at each on-treatment visit for all subjects except on Days 1, 3 and 5.

All subjects will be required to participate in an intensive serial PK sub-study to be performed on Day 1. The PK of SOF (and its metabolites GS-566500 and GS-331007), and VEL will be assessed. Serial PK samples will be collected at the following time points: 0 (pre-dose), 0.5, 1, 2, 4, 8, 12 and 24 hours post-dose.

---

---

**Statistical Methods:** The primary efficacy endpoint is the percentage of subjects who achieve SVR12 (HCV RNA < lower limit of quantitation [LLOQ] 12 weeks after stopping study drug) for subjects in the Full Analysis Set (FAS).

Secondary efficacy endpoints include the percentage of subjects who attain SVR at 4 weeks after cessation of treatment (SVR4); the percentage of subjects who have HCV RNA <LLOQ at each on-treatment visit; and the percentage of subjects with virologic failure (VF, defined as HCV RNA  $\geq$  LLOQ at end of treatment or relapse during the Post-treatment follow-up period).

The primary safety endpoint is the percentage of subjects who discontinue from study drug due to an adverse event. Deaths, graft loss, and rejection episodes will also be listed or summarized, as appropriate.

Other endpoints of interest include changes to immunosuppressive therapy and the emergence of viral resistance to SOF or VEL during and after cessation of treatment, and HCV RNA levels (IU/mL) at each on-treatment visit, if relevant.

---

This study will be conducted in accordance with the guidelines of Good Clinical Practice (GCP) including archiving of essential documents.

